6.4.2.2. Maintenance Dose

From Weeks 2 to 52, dose interruptions or adjustments will be performed within the maintenance dose range of $10\sim60~\mu g$ (Table 8) according to the dose adjustment algorithm (Table 9) so that the HemoCue Hgb value measured every other week will achieve or remain within the target range (10.0-12.0 g/dL). Dose adjustments will be made once every 2 weeks. If any of the one-step dose reduction criteria is met during treatment at the minimum maintenance dose ($10~\mu g$), treatment should be interrupted (and placebo administered); once the one-step dose increase criteria are met, treatment at $10~\mu g$ will be resumed. If the one-step dose increase criterion is met during treatment at the maximum maintenance dose ($60~\mu g$), treatment at $60~\mu g$ should be continued.

Table 8 Maintenance dose of darbepoetin alfa

Dose level	1	2	3	4	5	6
Darbepoetin alfa (once weekly)	10 μg	15 μg	20 μg	30 μg	40 μg	60 μg

Table 9 Dose adjustment algorithm (darbepoetin alfa)

Hgb (g/dL)	Treatment
>13.0	Interrupt treatment (and administer placebo) until Hgb decreases to less than
	12.0 g/dL, and resume treatment at the one lower dose level
	[If interrupted (and placebo administered) at 10 μg, resume treatment at 10 μg
	after the one-step dose increase criterion is met]
\geq 12.0 and \leq 13.0	One-step dose reduction
\geq 10.0 and <12.0	Continue treatment at the current dose level*
≥7.5 and <10.0	One-step dose increase**
<7.5	Discontinue treatment permanently*** and initiate another appropriate treatment

^{*} If an increase of 1 g/dL is observed in 2 weeks, the dose will be reduced to the one-step lower dose level.

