9.3. Data Analysis Considerations

9.3.1. Analysis Populations

• All Screening Population

The All Screening Population consists of all subjects who are given subject number and whose data are collected, including demographics at screening.

• Intention-To-Treat (ITT) Population

The ITT Population consists of all subjects who are given a randomization number regardless of whether they actually receive study treatment and whose Hgb assessment was performed at baseline and at least one scheduled post-baseline visit. Subjects will be analyzed according to randomized treatment. This population will be the primary population for an assessment of non-inferiority.

• modified ITT (mITT) Population

The mITT Population consists of all ITT subjects who have at least one Hgb measurement during the efficacy evaluation period. Subjects will be analyzed according to randomized treatment. This population will be the primary population for an assessment of superiority.

• Per-Protocol (PP) Population

The PP Population consists of all mITT subjects who are not major protocol violators. Details will be defined in the RAP. This population will be used for efficacy sensitivity analyses.

Safety Population

The Safety Population consists of subjects who receive at least one dose of study treatment. Subjects will be analyzed according to the treatment received. This population will be used for safety analyses.

• PK Population

The PK Population consists of all daprodustat -treated subjects from whom PK samples are collected and analyzed.

Additional populations may be defined in the RAP.

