## 4. ANALYSIS POPULATIONS

Population	Definition / Criteria	Analyses Evaluated
All Screening	
 
Consists of all subjects who are given subject number and are collected data at screening
 
	
 
Study Population
 

Enrolled	
 
Consists of subjects in 'All Screening' except for screen failures (who never passed screening even if rescreened)
 
	
 
Study Population (some displays for EudraCT)
 

Randomized	
 
Consists of all subjects who are given randomization number regardless of whether they actually receive study treatment
 
	
 
Study Population
 

Safety	
 
Consists of all subjects who receive at least one dose of study treatment.
 
Subjects will be analyzed according to the treatment received [1]
 
This population will be used for safety analyses.
 
	
 
Study Population
 
Safety
 

Intent-To-Treat (ITT)	
 
Consists of all Randomized subjects who have a baseline and at least one post baseline schedule Hgb assessment [2]
 
Subjects will be analyzed according to randomized treatment.
 
This population will be the primary population for an assessment of non-inferiority.
 
	
 
Study Population
 
Efficacy
 

modified ITT (mITT)	
 
Consists of all ITT subjects who have at least one Hgb measurement during the evaluation period.
 
Subjects will be analyzed according to randomized treatment.
 
This population will be the primary population for an assessment of superiority.
 
	
 
Study Population
 
Efficacy
 

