### NOTES:

- Basically, enrolled population will be the same as randomized population because a subject is going to be given randomized number as soon as passed screening.
  - Refer to [Appendix 10: List of Data Displays](#) which details the population used for each display
- [1]: Only subjects receiving incorrect randomized treatment for the duration of their study participation will be analyzed according to the treatment received. Otherwise, subjects will be analyzed according to the treatment to which they were randomized. Refer to [Appendix 10: List of Data Displays](#) which details the population used for each display.
- [2] See [Appendix 3](#) for the Hgb assessment to be used for analyses

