### 7.1.6.3. Tipping Point Analysis

The analyses will be based on the ITT population, unless otherwise specified.

Tipping point sensitivity analyses will be conducted under a range of missing data assumptions to determine how extreme assumptions need to be for non-inferiority conclusions to change. Assumptions about missing Hgb values on the daprodustat and darbepoetin alfa arm will vary independently, and will include scenarios where subjects with missing data on daprodustat have worse outcomes than subjects with missing data on darbepoetin alfa. If the tipping point scenario is clinically plausible, the conclusion under missing at random may be questionable.

In a strategy for intercurrent event of study withdrawal, a hypothetical scenario is considered to assess what would have happened if the event did not occur. For this hypothesis, the missing data due to this event would occur at not-at-random manner, that is the observations of missing depend on unobserved values, which will be mimicked with delta-adjustment analysis in this study.

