### Sensitivity and Supplementary Analyses

- The mITT Population will be used for this logistic analysis, and the supplementary analysis using same logistic model will be repeated in the ITT and PP Population to evaluate the robustness of the conclusion. In the ITT population, subjects who have no available Hgb after Week 40 will be considered as non-responder.
- The logistic regression will be performed by a set of pre-specified subgroups (Section 5.4.2). These subgroup analyses are considered exploratory to assess for consistency with the overall results.

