### 15.3. Appendix 3: Assessment Windows

All data will be reported according to the nominal visit date for which it was reported (that is, no visit windows will be applied during dataset creation). Permissible range at each visit was specified in time & event table (See [Appendix 2](#)). Records in the eCRF unscheduled visit will not be slotted to a particular time point, but remain as unscheduled if they are either summarized or listed unless otherwise specified.

Regarding the visits where only HemoCue Hgb is available (i.e., Week 2, Week 6, Week 10, etc. See [Appendix 2](#)), the Hgb values will not be used for any analyses but presented in the listing unless otherwise specified.

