## 16. REVISION HISTORY

Note that minor wording changes are not included in below.

Reporting and Analysis Plan_201754_Amendment_Final_V1.1 [06-Aug-2018]		
Section # and Name	Description of Change	Brief Rationale
4 Analysis Populations 15.3 Appendix 3: Assessment Windows	It has been clarified that Hgb assessments at HemoCue visits (Week 2, 6, 10, ...) will not be included in the analysis.	Clarification
5.4.2 Examination of Subgroups	Subgroup definitions for ERI and period of time on dialysis were refined.	It would facilitate review of subgroup results
6 Study Population Analyses 15.10.4 Table of Contents for SAC Deliverable	Some modifications were made for study population displays as below: 1. Added 2 listings; subjects excluded from any population and subjects excluded from per-protocol population 2. Removed a summary of race and racial combination based on ITT population. 3. Added a separate listing of study specific baseline characteristics	1. It would facilitate review of results of populations analyzed. 2. Safety population would be sufficient to be assessed 3. It would facilitate review of results of baseline characteristics.
6.2 Planned Summary Display Details	Clarifications has been made to the way to display of exposure and treatment compliance.	Clarification
7.1 Primary Efficacy Analyses 15.10.4 Table of Contents for SAC Deliverable	Added tables of the tipping point analysis	It would facilitate review of tipping point results.
7.1.6.3 Tipping Point Analysis	The number of imputations was reconsidered and a text was updated.	Modifications
7.2 Principal Secondary Efficacy Analyses	A method to construct 95% CI and a one-sided p-value for odds ratio has been specified in Section 7.2.5.1 Statistical Methodology Specification	Clarification

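### Two ITT analyses of withdrawal omit some of the earliest withdrawals because ITT entry needs a post-baseline Hgb, a requirement the SAP apparently tightens without listing the change

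*SAP*

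**What the plan says.** Protocol 9.3.1 admits to ITT a randomized subject, treated or not, "whose Hgb assessment was performed at baseline and at least one scheduled post-baseline visit". It limits neither the assay nor the visit. Week 2 is a scheduled visit with a HemoCue Hgb (Protocol 7.1, Table 10).

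SAP Section 4 uses nearly the same words: "Consists of all Randomized subjects who have a baseline and at least one post baseline schedule Hgb assessment [2". The mark at the end is note [2], which sends the reader to Appendix 3 "for the Hgb assessment to be used for analyses". For visits that have only a HemoCue value, Week 2 among them, Appendix 3 states that "the Hgb values will not be used for any analyses but presented in the listing unless otherwise specified". The SAP revision history enters this rule against Section 4 as well as Appendix 3, and labels it a clarification: "It has been clarified that Hgb assessments at HemoCue visits (Week 2, 6, 10, ...) will not be included in the analysis". Note [4] to SAP Figure 1, however, describes who falls outside ITT with no limit on assay or visit. SAP Table 1, the list of changes to the protocol's analysis plan, has a single entry, on multiplicity.

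Two analyses that address withdrawal use this population:

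- Tipping point (SAP 7.1.6.3): "The analyses will be based on the ITT population, unless otherwise specified".
- Supplementary responder analysis (SAP 7.2.5.1): "In the ITT population, subjects who have no available Hgb after Week 40 will be considered as non-responder".

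**The concern.** Whether a subject enters ITT depends on something that happens after randomization, namely staying long enough to give a qualifying Hgb. The primary MMRM loses nothing by this, since its first modelled visit is Week 4. The tipping-point and non-responder analyses are different. They exist to show what withdrawal could do to the conclusions, and neither needs a post-baseline value.

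In the tipping-point analysis the subjects left out are those who would carry the largest adjustment, because delta accumulates with every missed visit. In the responder analysis, SAP 7.2.4 treats early withdrawal as failure, but mITT excludes by definition anyone without an Hgb in Weeks 40 to 52. Only the ITT run can apply the rule to them, and it omits the earliest.

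Equal early loss in the two arms cannot be taken for granted. Daprodustat stays at its starting dose until Week 4 (Protocol 6.4.1.1), while darbepoetin alfa is adjusted from Week 2 "so that the HemoCue Hgb value measured every other week will achieve or remain within the target range" (Protocol 6.4.2.2). If more subjects leave one arm early, omitting them flatters that arm.

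**Working it through.** **1. The plan's own figures.** Inputs from Protocol 9.2.1: margin -1.0 g/dL, true difference 0, SD 1.5, 100 per group, one-sided 2.5%, 25% dropout.

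- Power by noncentral t is 99.68% (stated as 99.7% in Table 13).
- 100 / (1 - 0.25) = 133.3, so 134 per group (stated as approximately 135).
- Smallest passing difference: -(1 - 1.972 × 1.5 × √(2/100)) = -(1 - 0.418) = -0.582 (as stated).

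All reproduce, and none depends on the ITT definition.

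**2. Who is in ITT.**

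| Only post-baseline Hgb | Protocol 9.3.1 | SAP 4 with note [2] and Appendix 3 |
|---|---|---|
| None | Out | Out |
| Week 2 HemoCue | In | Apparently out |
| Early-withdrawal or follow-up sample | Not stated | Not settled |
| Week 4 or later scheduled visit | In | In |

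On the third row, Protocol Table 10 has hematology at both the early-withdrawal and follow-up visits. SAP Appendix 3 lists Follow-up as an analysis time point, and SAP 15.6.3 calls it a scheduled visit. Early withdrawal is not in the Appendix 3 list.

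**3. What each method needs.** In SAP 7.1.6.3 the first visit is imputed within arm from baseline Hgb alone. The nth missed visit then receives n × delta. For a subject with no modelled visit, Week 40 is the tenth (40/4), so delta = -0.4 subtracts 4.0 g/dL and takes an assumed 11.0 to the SAP's 7.0 floor. The responder rule needs only the absence of Hgb after Week 40.

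**4. How many.** The documents give no timing for dropout. I assume a constant rate reaching 25% at Week 52.

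- Before Week 2: 135 × (1 - 0.75^(2/52)) = 135 × 0.0110 = 1.5 per arm, outside ITT in both documents.
- Before Week 4: 135 × (1 - 0.75^(4/52)) = 135 × 0.0219 = 3.0 per arm.
- Due to the SAP narrowing: 3.0 - 1.5 = about 1.5 per arm.

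Fewer are lost if follow-up Hgb counts. If 5% left this early (assumed), it would be 0.05 × 135 = 6.75, about 7 per arm.

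**5. Effect on the tipping point.** Restoring k daprodustat subjects at 7.0 instead of 11.0 moves the arm mean by -4k/135: -0.03 (k = 1), -0.09 (k = 3), -0.21 (k = 7), against a margin of 1.0. In an extreme corner, all 34 expected daprodustat dropouts sit at 7.0, and the remaining 101 subjects and the comparator at 11.0:

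| Daprodustat subjects omitted | Difference in means (g/dL) |
|---|---|
| 0 | 34 × (-4)/135 = -1.01 |
| 1.5 | 32.5 × (-4)/133.5 = -0.97 |
| 3 | 31 × (-4)/132 = -0.94 |

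These are point differences. With a half-width near the design's 0.418, non-inferiority fails in every row, so the table shows the size of the shift and not a reversal.

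**6. Effect on the responder analysis.** Assume 108 per arm reach Week 40 (135 × 0.75^(40/52)), with 90% and 75% in range, giving 97 and 81 responders. Unadjusted odds ratios with Wald 95% CI:

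| Subjects analysed (daprodustat / darbepoetin alfa) | Odds ratio (95% CI) |
|---|---|
| 135 / 135, all randomized | 1.70 (1.02 to 2.83) |
| 132 / 132, three omitted per arm | 1.74 (1.04 to 2.94) |
| 129 / 135, six omitted from daprodustat only | 2.02 (1.19 to 3.42) |

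**The case against.** The case for leaving this alone is substantial, and much of it stands.

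- A reader might infer that the SAP drops every subject without a Week 4 or later Hgb. The documents do not establish that. A follow-up Hgb after withdrawal could satisfy the literal SAP wording, and Figure 1 note [4] carries no restriction.
- A reader might also infer that the SAP narrowing explains all the missing early withdrawals. It does not. Anyone who leaves before Week 2 with no post-baseline Hgb fails Protocol 9.3.1 too, so aligning the SAP with the protocol would not recover them.
- Protocol 7.3 makes central-laboratory Hgb the main efficacy measure and assigns HemoCue to eligibility, discontinuation and dosing. Calling the rule a clarification is therefore defensible, and the revision history discloses it. The gap is its absence from Table 1 and the mismatch with note [4].
- The tipping-point analysis varies delta in both arms and both directions, so it is not purely a penalty on withdrawal. No document reports different early loss by arm.
- A subject stopped at Week 2 for Hgb below 7.5 g/dL would be unusual, since entry requires at least 9.5, a fall of more than 2 g/dL in two weeks.
- Neither affected analysis carries a success rule, and Table 1.7 and Listing 8 will show exclusions.
- Not every randomized subject can be analysed. If the Day 1 Hgb is missing, baseline is missing (SAP 5.2), and both models use baseline. The fix allows for this.

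None of this gives a reason to omit subjects whom both methods can handle.

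**Conclusion.** The point holds in a limited form. Both ITT definitions require a post-baseline Hgb, so two analyses about withdrawal leave out some of the earliest withdrawals without needing to. The SAP apparently narrows the set further by excluding a Week 2 HemoCue value as the qualifying Hgb. It contradicts its own Figure 1 note in doing so, and does not record the change in Table 1. Whether an early-withdrawal or follow-up value qualifies is open.

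Under the constant-rate assumption this concerns about 3 of 135 per arm, roughly half of them because of the SAP. With balanced losses the effect is minor: the illustrative odds ratio is 1.74 instead of 1.70. It grows only if early losses are concentrated in one arm, which the documents neither show nor exclude. It would be wrong to infer a bias in the primary result. Subjects with no Hgb from Week 4 on contribute nothing to the MMRM, and the principal secondary analysis uses mITT. This is a cheap improvement to supplementary analyses and does not threaten the main conclusions.

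**What to change.** - Run Tables 2.12 and 2.17 and Figure 2.9 on all Randomized subjects (a population already defined in SAP Section 4) who have a Day 1 Hgb. For the tipping point, impute from baseline Hgb within arm. For the responder analysis, score subjects with no Hgb after Week 40 as non-responders.
- Report the number of randomized subjects without a baseline Hgb separately, by arm.
- Reconcile SAP Section 4 note [2], SAP Figure 1 note [4] and Protocol 9.3.1. State whether Week 2 HemoCue, early-withdrawal and follow-up Hgb values qualify a subject for ITT.
- If the narrower set is kept for other ITT displays, list it in SAP Table 1.
- Leave the primary MMRM and the mITT principal secondary analysis as they are.

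The cost is some SAP wording and a changed population label on two tables and one figure. No new data are needed. The supplementary results may come out slightly less favourable.

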### NOTES:

- Basically, enrolled population will be the same as randomized population because a subject is going to be given randomized number as soon as passed screening.
  - Refer to [Appendix 10: List of Data Displays](#) which details the population used for each display
- [1]: Only subjects receiving incorrect randomized treatment for the duration of their study participation will be analyzed according to the treatment received. Otherwise, subjects will be analyzed according to the treatment to which they were randomized. Refer to [Appendix 10: List of Data Displays](#) which details the population used for each display.
- [2] See [Appendix 3](#) for the Hgb assessment to be used for analyses

**Figure 1 Analysis Populations**

**NOTES:**

- [1]: Subjects who never passed screening even if rescreened
- [2]: Subjects who are not given randomization number
- [3]: Subjects who never receive study treatment
- [4]: Subjects who do not have Hgb measurement at both baseline and at least one scheduled visits following the baseline
- [5]: Subjects who have no Hgb measurement during the efficacy evaluation period
- [6]: Subjects who are major protocol violators (See Section 4.1 and [Appendix 1](#))

**4.1. Protocol Deviations**

Important protocol deviations (including deviations related to study the inclusion/exclusion criteria, conduct of the trial, patient management or patient assessment) will be summarized and listed.

Important deviations which resulted in exclusion from the analysis population will also be summarized and listed (Please refer to [Appendix 1: Protocol Deviation Management and Definitions for Per Protocol Population](#)).

Protocol deviations will be tracked by the study team throughout the conduct of the study in accordance with the Protocol Deviation Management Plan (PDMP).

- Data will be reviewed prior to freezing the database to ensure all important deviations and deviations which may lead to exclusion from the analysis are captured and categorized on the protocol deviations dataset.
- This dataset will be the basis for the summaries and listings of protocol deviations.

A separate summary and listing of all inclusion/exclusion criteria deviations will also be provided. This summary will be based on data as recorded on the inclusion/exclusion page of the eCRF.

## 5. CONSIDERATIONS FOR DATA ANALYSES AND DATA HANDLING CONVENTIONS

### 5.1. Study Treatment & Sub-group Display Descriptors

Treatment Group Descriptions			
RandAll NG		Data Displays for Reporting	
Code	Description	Description	Order in TLF
D1	Daprodustat	Daprodustat	1
D2	Darbepoetin alfa	Darbepoetin alfa	2

Treatment comparisons will be displayed as follows using the descriptors as specified:

1. Daprodustat vs Darbepoetin Alfa

### 5.2. Baseline Definitions

The baseline Hgb value will be the value from the Day 1 visit. If missing at Day 1 visit, the baseline will be set to missing.

For all other endpoints, the baseline value will be the latest pre-dose assessment with a non-missing value. This is generally expected to be the pre-dose value from the Day 1 visit, except for ECG. For ECG, screening assessment will be used as a baseline. The baseline value of vital signs at pre- and post-dialysis will be defined separately. If missing at Day 1 visit, screening assessment or other pre-dose assessment may be used as baseline. If baseline data is missing (i.e. Day 1, screening, and pre-dose assessment is all missing), no derivation will be performed and baseline will be set to missing.

Definition	Reporting Details
Change from Baseline	= Post-Dose Visit Value – Baseline
Change from Baseline For Vital Signs	
 
• Pre-dialysis: = Post-Dose Visit Value from Pre-Dialysis Assessment – Baseline from Pre-Dialysis Assessment
 
• Post-dialysis: = Post-Dose Visit Value from Post-Dialysis Assessment – Baseline from Post-Dialysis Assessment
 

% Change from Baseline	1. Log-transform the data at both the baseline and the specified

Definition	Reporting Details
For TSAT, Hcpidin, and Lipid Parameters	
timepoint
 
 
2. Calculate a change from baseline using the log-transformed data for each subject
 
3. Calculate the mean, and 95% CI and standard error (SE) of the log-transformed data
 
4. Exponentially back-transform to the original scale
 
5. Subtract 1, then multiply everything by 100%
 
 
So, geometric mean for percent change from baseline  <math>= \{ \exp(\text{Mean} [\ln(\text{Post-Dose Visit Value}) - \ln(\text{Baseline})]) - 1 \} \times 100</math>
 
Coefficient of variation will be calculated as  <math>\text{CV}\% = [\exp(\text{Var in loge scale}) - 1]^{1/2} \times 100</math>            where 'Var in loge scale' represents variance of percent change from baseline in loge scale.

### 5.3. Multicenter Studies

It is anticipated that subject accrual will be spread thinly across centers and summaries of data by center would be unlikely to be informative. Therefore, data from all participating centers will be just pooled for analysis.

